5.6 Key Definitions

Baseline value is defined as the last available off-treatment value collected prior to the time of the first dose.

Relative study day is defined as number of days from the first dose date and will be presented on all listings where a complete date is presented.

6 SUBJECT DISPOSITION AND BASELINE CHARACTERISTICS

6.1 Subject Discontinuation

The number of subjects who enroll in the study and the number and percentage of subjects who complete the study will be presented by treatment. The frequency and percentage of subjects who withdraw or discontinue from the study and the primary reason for withdrawal or discontinuation will be summarized.

A data listing of subject disposition including study completion status and reason for study discontinuation will be provided. In addition, subject populations and reasons for exclusion from the population will be provided in a data listing.

6.2 Protocol Deviations

Protocol deviations will be captured as a log from clinical monitoring and presented in a data listing.

6.3 Demographics and Baseline Characteristics

Descriptive statistics (ie, mean, SD, median, minimum, and maximum) will be calculated for continuous demographic and baseline characteristics variables (age, weight at Screening, height, and body mass index at Screening) and frequency counts and percentages will be tabulated for categorical demographic variables (sex, race, and ethnicity) for each treatment and overall.

A data listing will be provided for all demographic data. In addition, the baseline characteristics of weight, height, and body mass index will be included in the vital sign data listing.

6.4 Medical History

Medical history data will be mapped using the current version of Medical Dictionary for Regulatory Activities (MedDRA) to system organ class (SOC) and preferred term (PT) and will be listed by subject identification number, medical condition reported term, onset date, and ongoing status/resolution date.

6.5 Inclusion and Exclusion Criteria

Inclusion and exclusion criteria not met will be provided in a data listing.

7 PHARMACOKINETIC ANALYSES

7.1 Moxidectin and Metabolite Concentrations

Moxidectin concentrations in plasma will be collected and analyzed for all subjects. Moxidectin concentrations in urine and feces and metabolite concentrations in plasma and urine will be analyzed for the subset of subjects who receive the 8-mg dose (See Table 3).

Table 3. Analyses for Each Matrix

Matrix	Analysis for moxidectin	Analysis for moxidectin metabolites
Plasma	✓ ^a	✓ ^b
Urine	✓ ^b	✓ ^b
Feces	✓ ^b	not analyzed

^a All subjects ^b 8-mg cohort

For plasma, the time course of concentrations of moxidectin will be presented and summarized using descriptive statistics (n, mean, SD, CV%, median, minimum, maximum, geometric mean, and geometric CV%) by time point and treatment. For urine and feces, the amount of moxidectin excreted by collection interval will be presented and summarized using descriptive statistics (n, mean, SD, CV%, median, minimum, maximum, geometric mean, and geometric CV%) by time point and treatment.

For plasma and urine, amount of metabolite by collection interval and metabolite to parent (molar equivalents) ratios will be presented and summarized using descriptive statistics (n, mean, SD, CV%, median, minimum, maximum, geometric mean, and geometric CV%) by collection interval and treatment.

Concentrations that are BQL will be treated as outlined in Section 5.5. Mean plasma concentration-time profiles will be plotted by treatment on linear and semilogarithmic scales using nominal times. Individual concentration-time plots and spaghetti plots with subject concentration-time profiles overlaid by respective treatments will be included in the appendices using linear and semilogarithmic scales.

7.2 Pharmacokinetic Parameters

All PK analyses will be performed according to applicable standard operating procedures and protocol specifications. Pharmacokinetic parameters will be calculated for the PK population using Phoenix[®] WinNonlin[®] version 6.3 or later (Certara, Princeton, New Jersey) using actual sampling times. If actual times are missing, nominal times may be used and will be noted in the appropriate data listing.

The PK parameters for plasma moxidectin will be estimated as follows (data permitting):

AUC _{0-last} :	AUC from time 0 extrapolated to the last observed concentration, calculated by a combination of linear and logarithmic trapezoidal methods (linear up/log down method).
AUC _{0-inf} :	AUC from time 0 extrapolated to infinity, calculated as AUC _{0-last} + C _{last} /λ _z where, C _{last} is the last measurable concentration.
AUC _{ext} :	Percentage of AUC _{0-inf} obtained by extrapolation, calculated as [(AUC _{0-inf} – AUC _{0-last})/AUC _{0-inf}] * 100 (a diagnostic parameter calculated and listed in the data listing, but not included in the descriptive statistics).
AUC ₀₋₂₄ :	AUC from time 0 to 24 hours.
AUC ₀₋₄₈ :	AUC from time 0 to 48 hours.
AUC ₀₋₇₂ :	AUC from time 0 to 72 hours.
AUC ₂₄₋₄₈ :	AUC from time 24 to 48 hours.
AUC ₄₈₋₇₂ :	AUC from time 48 to 72 hours.
C _{max} :	Maximum observed plasma concentration, observed by inspection of individual study participant plasma concentration-time plots.
T _{max} :	Time to C _{max} , obtained directly from the observed concentration-time data.
t _{1/2} :	Terminal elimination half-life, calculated using the equation (ln[2]/λ _z).
λ _z :	Terminal elimination rate constant, estimated by linear regression of logarithmically transformed concentration-time data. Calculation of λ _z requires a minimum of 3 data points after (and not including) C _{max} . The coefficient of determination (R ²), for the linear regression must be at least 0.95.
CL/F:	Apparent clearance following extravascular administration, calculated as Dose/AUC _{0-inf} .
V _d /F	Apparent volume of distribution following extravascular administration, calculated as Dose/(λ _z * AUC _{0-inf}).

All subjects in the PK population will be included in the descriptive statistics for the PK parameters. No value for λ_z, AUC_{0-inf}, AUC_{ext}, CL/F, V_d/F, or t_{1/2} will be reported for cases that do not exhibit a terminal log-linear phase in the concentration-time profile. No PK parameters will be calculated for subjects with fewer than 4 quantifiable concentrations following BQL imputation. Additional PK parameters may be calculated, as necessary, to fully characterize the PK profile of moxidectin.

The PK parameters for urine moxidectin will be estimated as follows (data permitting):

$Ae_{urine(0-72)}$:	Urinary recovery between 0 and 72 hours, where $Ae_{(0-t)} = \sum_{n=1}^t (C_{urine,i} * V_{urine,i})$, where $C_{urine,i}$ represents the concentration of drug in urine during collection interval i, and $V_{urine,i}$ represents the cumulative urine volume during collection interval i.
$Ae_{urine(0-24)}$:	Urinary recovery between 0 and 24 hours, where $Ae_{(0-24)} = C_{urine(0-24)} * V_{urine(0-24)}$.
$Ae_{urine(24-48)}$:	Urinary recovery between 24 and 48 hours, where $Ae_{(24-48)} = C_{urine(24-48)} * V_{urine(24-48)}$.
$Ae_{urine(48-72)}$:	Urinary recovery between 48 and 72 hours, where $Ae_{(48-72)} = C_{urine(48-72)} * V_{urine(48-72)}$.
$CL_{r(0-72)}$:	Renal clearance from 0 to 72 hours, where $Ae_{(0-72)}/AUC_{(0-72)}$.
$CL_{r(0-24)}$:	Renal clearance from 0 to 24 hours, where $Ae_{(0-24)}/AUC_{(0-24)}$.
$CL_{r(24-48)}$:	Renal clearance from 24 to 48 hours, where $Ae_{(24-48)}/AUC_{(24-48)}$.
$CL_{r(48-72)}$:	Renal clearance from 48 to 72 hours, where $Ae_{(48-72)}/AUC_{(48-72)}$.

The PK parameters for feces moxidectin will be estimated as follows (data permitting):

$Ae_{feces(0-72)}$:	Fecal recovery between 0 and 72 hours, where $Ae_{(0-t)} = \sum_{n=1}^t (C_{feces,i} * W_{feces,i})$, where $C_{feces,i}$ represents the concentration of drug in feces (ng/g) during collection interval i, and $W_{feces,i}$ represents the total fecal mass during collection interval i.
$Ae_{feces(0-24)}$:	Fecal recovery between 0 and 24 hours, where $Ae_{(0-24)} = C_{feces(0-24)} * W_{feces(0-24)}$.
$Ae_{feces(24-48)}$:	Fecal recovery between 24 and 48 hours, where $Ae_{(24-48)} = C_{feces(24-48)} * W_{feces(24-48)}$.
$Ae_{feces(48-72)}$:	Fecal recovery between 48 and 72 hours, where $Ae_{(48-72)} = C_{feces(48-72)} * W_{feces(48-72)}$.

Descriptive statistics of PK parameters for moxidectin will be provided for the PK population by treatment and will include n, mean, SD, CV%, median, minimum, maximum, geometric mean, and geometric CV% (where applicable).

8 PHARMACODYNAMIC ANALYSES

The PD analyses for the continuous 12-lead ECG data is outlined in this section, but will be the responsibility of Mason Cardiac Safety Consultation.

8.1 Continuous 12-Lead Electrocardiogram Assessments

Pharmacodynamics will be assessed via ECGs obtained using a Mortara continuous 12-lead digital ECG recorder, which will be reviewed and analyzed by the central ECG laboratory. The device will remain connected to the subject during the confinement period. The ECG data will be transmitted wirelessly to the Surveyor system, which will extract triplicate 10-second ECG recordings (approximately 1 minute apart) at baseline (before dosing) and at 0.5, 1, 2, 3, 4, 5, 6, 8, 12, 24, 36, 48, 60, and 72 hours after dosing. A window of ± 5 minutes around each time point will be utilized to capture ECGs of adequate quality, although every effort should be made to capture them as close to the scheduled time points as possible. The ECG extractions will be time-matched to the PK samples but obtained before the actual sampling time to avoid changes in autonomic tone associated with the psychological aspects of blood collection as well as the reduction in blood volume subsequent to blood collection.

The continuous ECG data will be sent to the central ECG laboratory for a high-resolution measurement of the cardiac intervals and morphological assessment. The ECG core laboratory staff will be blinded to treatment, time, and study day identifiers.

The 12-lead continuous digital ECG signal for each subject will be recorded continuously during subject confinement.

Digital ECGs will be transmitted to the central ECG laboratory's validated data management system. If targeted ECG time points are artifactual and of poor quality, the central ECG laboratory will extract analyzable 10-second ECGs as close as possible to the targeted time points. The cardiologists responsible for interpreting the ECGs will be blinded to all study drug identifiers and collection times.

Lead II is the lead of choice for the over-reads and the baseline and on-treatment ECGs will be based on the same lead. All ECGs from a particular subject will be read by a single reader.

If lead II is not analyzable, ECG analysis will be conducted in lead V₅. If lead V₅ is not analyzable, the most appropriate lead will be used (eg, lead V₂).

8.2 General Summaries

All continuous 12-lead ECG data collected will be presented in data listings. Data from subjects excluded from the analysis populations will be presented in the data listings, but not included in the calculation of summary statistics. For categorical variables, frequencies and percentages will be presented. Continuous variables will be summarized using descriptive statistics (n, mean, SD, 2-sided confidence bounds [90% for the QTcF interval or 95% for other parameters], median, 25th percentile, 75th percentile, minimum, and maximum). The mean of the triplicate 0-hour time point on Day 1 will be used as the

baseline. The continuous 12-lead ECG parameters (QTcF, HR, PR, RR, and QRS) and the corresponding changes from Baseline (denoted as dQTcF, dHR, dPR, dRR, and dQRS) and placebo-adjusted endpoints (denoted as ddQTcF, ddHR, ddPR, ddRR, and ddQRS) will be summarized by treatment and time point.

The means and 90% CIs for the dQTcF and placebo-adjusted (algebraic) ddQTcF will be calculated across all subjects for each time point and each active treatment and displayed graphically. Secondary endpoints will also be displayed using 95% CI, if applicable.

8.3 Statistical Analyses

Primary Analysis

The relationship between time-matched, baseline-adjusted QTcF (dQTcF) and moxidectin concentrations will be investigated by linear mixed-effects modeling. The ddQTcF value will be calculated as the placebo-corrected dQTcF estimated from the model.

Before modeling, the concentration-ddQTcF relationship will be explored graphically to determine the presence of hysteresis. Hysteresis will be assumed if, on average (or median), there are at least 3 time points with ddQTcF >5 msec and the time to maximum observed plasma concentration (T_{max}) and the time of maximal ddQTcF (U_{max}) differ by 30 minutes or more and the 1-sided, 1-sample Wilcoxon test for the difference between ddQTcF at T_{max} and at U_{max} is significant at the 1% level. If hysteresis is present, the possibility of fitting a population PK model with an effect compartment will be explored.

The primary analysis will be provided for the ECG population using a mixed-effects model with dQTcF as the dependent variable and treatment (active and placebo), time point, and treatment by time point interaction as the independent variables with baseline QTcF as a covariate and time-matched concentrations of moxidectin (observed if hysteresis is not present; predicted from the effect compartment if hysteresis is present) as a covariate with random effects of intercept and slope. Concentrations of zero will be used for the placebo treatment. A spatial power law covariance structure (a time-dependent first-order autoregressive covariance designed for unequally-spaced time points) will be used. If the model does not converge then unstructured (UN) or compound symmetry (CS) structures will be assessed, in that order. The model will be used for predicting population average and 90% 2-sided bootstrapped CI of the baseline-adjusted difference (ie, ddQTcF) between active and placebo at each time point bound at clinically relevant concentrations. The bootstrap method will be based on percentile CI using the 5th and 95th percentiles in the resampling distribution using 1000 iterations.

The criterion for negative QT assessment will be the upper bound of the 2-sided 90% bootstrapped CI for ddQTcF being below 10 msec at the largest geometric mean C_{max} value. In addition, the significance and magnitude of parameter estimates of the treatment covariate (active vs. placebo) will be considered.

At the request of the United States Food and Drug Administration, the primary endpoint in the study has been updated to dQTcF and this is the dependent variable in the primary analysis, which includes plasma concentrations as covariates with random slope and intercept as well as treatment and time point as categorical independent variables. However, in addition to obtaining the plasma concentration intercept and slope estimates, the estimated dQTcF values from the primary analysis will be compared by calculating the differences overall and at each time point between the active treatment and placebo, resulting in estimates of ddQTcF, which will be presented. In addition, a secondary analysis with ddQTcF as the dependent variable will be performed, as is typical and well understood, to assess correlation and overall profile of ddQTcF and plasma concentrations. We believe it is important to do these analyses in addition to the primary analysis, because the dQTcF analysis could yield a spuriously positive or negative regression slope based on the relationship between the well-known spontaneous circadian change in dQTcF and the concentration-time profile of the investigational drug. For example, if the early to midday circadian increase in dQTcF concurred with a rise in plasma concentration of moxidectin, this could create the appearance of a positive relationship that might exceed the upper confidence boundary of 10 msec within the drug's clinically-expected concentration range. Converse timing between circadian change and plasma concentration change could produce the opposite effect. In the ddQTcF analysis, the placebo group's circadian change largely eliminates this type of spurious observation. Thus, in addition to examining the dQTcF model, if the primary analysis produces a significantly positive or negative regression slope, we will also examine the relationship between the investigational drug's plasma concentration-time course in relationship to the circadian change of dQTcF in the placebo group, to determine if a positive or negative correlation could have affected the dQTcF-plasma concentration relationship.

The relevant SAS code statements are:

```
PROC MIXED DATA = DATA;  
  CLASS SUBJID TRT ATPTN;  
  MODEL dQTcF = BASE TRT ATPTN TRT*ATPTN CONC /SOLUTION  
RESIDUAL OUTP=PRED;  
  RANDOM INTERCEPT CONC / SUBJECT = SUBJID;  
  REPEATED ATPTN / type=SP(POW) (ATPTN) SUBJECT=SUBJID;  
  LSMEANS TRT TRT*ATPTN /DIFF ALPHA=0.1 CL at CONC=xx.x;  
  LSMEANS TRT TRT*ATPTN /DIFF ALPHA=0.1 CL;  
RUN;
```

In the above statements:

- TRT represents the treatment (active or placebo);
- ATPTN represents the postdose nominal time point;
- BASE represents the baseline value for QTcF;
- CONC represents measured plasma concentrations of moxidectin;

- SP(POW) is a spatial power law covariance structure (a time-dependent first-order autoregressive covariance designed for unequally-spaced time points), if the model does not converge then unstructured or compound symmetry structures will be assessed, in that order;
- LSMEAN differences between the treatments at the Geometric C_{\max} value and at the average concentration value, where xx.x represents the largest geometric mean C_{\max} value among the doses, most likely for the 36-mg dose, will be provided.

Model assumptions will be reviewed with plots of standardized residuals versus fitted values and normal Q-Q plots of the standardized residuals. If nonlinearity is present, a log linear and/or maximum effect (E_{\max}) or other model will be considered.

Similar analyses will be repeated for HR, PR, and QRS, however, bootstrap percentiles will be based on the 2.5th and 97.5th percentiles, corresponding to a 2-sided 95% CI rather than the 2-sided 90% CI.

Secondary Analysis: Pharmacokinetic/Pharmacodynamic Analyses

To evaluate the relationship between placebo-corrected mean change from Baseline in QTcF (ie, ddQTcF) versus plasma concentrations of moxidectin for all subjects in the PK/PD population, both graphical and mixed-effects analyses of plasma concentration of ddQTcF versus plasma concentration of moxidectin will be performed. The mixed-effects model will be used to account for the clustering effects within each subject at different time points. The mixed-effects model will contain ddQTcF as the dependent variable and include the corresponding time-matched plasma moxidectin concentrations as the independent variable. The mixed-effects model will be used to estimate, for all subjects, the predicted population mean ddQTcF and its corresponding upper 95% 1-sided (equivalent to the upper 90% 2-sided) CI over a range of observed plasma concentrations. A negative result (ie, the model indicates no plasma concentration effect) is a slope of approximately zero.

The adequacy of the linear assumption between ddQTcF and plasma concentrations will be determined by adding a quadratic term to the mixed-effects model. If the quadratic term is different than zero, having $P < 0.05$, and Akaike's information criterion (AIC) is smaller in comparison with the linear model's AIC, then a quadratic term may be added. In addition, a transformation of the concentrations (eg, $\log[C/LLOQ]$, where LLOQ is the lower limit of quantitation of the assay and all values below the LLOQ are replaced with the LLOQ) may also be assessed. The best model fit will be determined by the lowest AIC.

The predicted mean expected ddQTcF and the 90% 2-sided CI will be calculated using the estimates of the slopes from the mixed-effect models, for all subjects, at relevant concentration levels (ie, the mean maximum plasma concentration under each dose level).

The relevant SAS code statements are:

```
PROC MIXED DATA = DATA;  
  CLASS SUBJID;  
  MODEL ddQTcF = CONC /SOLUTION OUTPM=PRED ALPHA=0.05;  
  RANDOM INTERCEPT CONC / TYPE=UN SUBJECT = SUBJID;  
RUN;
```

In the above statements:

- CONC represents the measured plasma concentrations of moxidectin;
- Type=UN means an unstructured covariance matrix, which is used for the correlated random effects (INTERCEPT and CONC). If the model does not converge other covariance structures will be investigated.

A plot will be provided to show CI of each treatment using the following model, adding in the treatment variable as follows:

```
PROC MIXED DATA = DATA;  
  CLASS SUBJID TRT;  
  MODEL ddQTcF = CONC TRT/SOLUTION OUTP=PRED;  
  RANDOM INTERCEPT CONC /TYPE=UN SUBJECT = SUBJID;  
RUN;
```

Where TRT represents the individual treatments (moxidectin 4 mg, moxidectin 8 mg, moxidectin 16 mg, moxidectin 24 mg, and moxidectin 36 mg).

A plot of the observed median-decile drug concentrations and associated mean ddQTcF (90% CI) together with the mean model-predicted ddQTcF will be used to evaluate the adequacy of the model fit to the assumption of linearity and the impact on quantifying the concentration response relationship.

Categorical QTc Findings

Categorical summaries using the largest postdose QTcF and largest change from Baseline (dQTcF) will be performed to determine the number and percentage of subjects, by treatment, who meet each of the following criteria:

- Result ≤ 450 msec;
- Result > 450 and ≤ 480 msec;
- Result > 480 and ≤ 500 msec;
- Result > 500 msec;
- dQTcF ≤ 30 msec;
- dQTcF > 30 and ≤ 60 msec;
- dQTcF > 60 msec.

Categorical Analysis of Other ECG Intervals

Categorical summaries of outliers will be provided for other ECG variables (PR, QRS, and HR) as follows:

- PR outliers postdose (PR >200 msec and a 25% or greater increase from Baseline);
- QRS outliers postdose (QRS >100 msec and a 25% or greater increase from Baseline);
- HR outliers postdose (HR <50 beats/minute and a 25% or greater decrease from Baseline);
- HR outliers postdose (HR >100 beats/minute and a 25% or greater increase from Baseline).

Any instance in 1, 2, or 3 of the triplicate ECGs of any subject overall and at each time point will be counted as 1 outlier event.

ECG Diagnostic Statement Analysis

Abnormal diagnostic statements will be tallied and tabulated for each treatment and time point. The variety of diagnostic statements with the same meaning will be aggregated into defined categories. For example, T wave inversion and lead V₂ and T wave flattening in lead II will both be categorized as nonspecific T wave abnormality. The incidence rate of diagnostic statements will be tabulated for both predose and postdose assessments, and also tabulated with diagnostic statements categorized as treatment-emergent diagnostic statements (ie, diagnostic statements not present on any baseline assessment). All abnormal ECG diagnostic findings will be listed.

Adequacy of HR Correction

The adequacy of the correction formula will be assessed by determining the linear relationship of QTcF to RR. Adequacy is defined as a population QTcF:RR slope of <|0.045|, and a slope of <|0.045| in at least 50% of individual subjects.

The QT interval with individual correction (QTcI) is mentioned in the International Council for Harmonisation E14 Guidance as an ancillary correction method.

The QTcI, if needed, will be calculated for each subject, using all available QT/RR predose pairs by first determining the slope of each subject's QT:RR relationship using all available predose data. Then QTcI will be calculated from each subject's individual ECG time point QT and RR interval values with the formula: $QTcI = QT + \text{slope} (1000 - RR)$.

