2.4.2 Pharmacodynamic Endpoints

The PD endpoints are calculated from the mean of the triplicate continuous 12-lead ECG data as:

1. $dQTcF$ – baseline-adjusted QT interval corrected by Fridericia's formula ($QTcF$);
2. $ddQTcF$ – time-matched, placebo-corrected, baseline-adjusted $QTcF$, which is calculated as the $dQTcF$ minus the time-matched mean $dQTcF$ of all placebo subjects at each postdose time point ($ddQTcF=[dQTcF(\text{active dose groups})-\text{mean } dQTcF(\text{placebo})]$);

The primary study endpoint is the $dQTcF$ matched to the plasma concentration of moxidectin collected at the same time point.

Analogous-derived exploratory endpoints are also calculated for heart rate (HR), and duration of PR, RR, and QRS interval parameters.

The ECG morphologic changes data are also considered an exploratory endpoint.

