3.2 Sample Size Considerations

The sample size of 60 subjects (10 subjects each in 6 treatment groups) is considered adequate to explore the effects of moxidectin on the corrected QT interval (QTc), as this design will yield 900 QTc-PK pairs in total. Additional subjects may be enrolled as alternates in this study should a subject choose to withdraw consent before study drug administration. Alternate subjects will remain in the clinical research unit (CRU) from Check-in until all subjects due to be dosed have completed dosing. Subjects who withdraw after dosing will not be replaced.

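### The 1% hysteresis test compares a maximum picked from the same data, so 1% is not its error rate; a false result changes the primary covariate but probably moves the QT estimate little

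*SAP*

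**What the plan says.** SAP section 8.3, Primary Analysis, assumes hysteresis when three conditions hold together, introduced as applying on average or to the median:

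- "there are at least 3 time points with ddQTcF >5 msec";
- Tmax and "the time of maximal ddQTcF (U_{max}) differ by 30 minutes or more";
- "the 1-sided, 1-sample Wilcoxon test for the difference between ddQTcF" at those two times, which counts if it "is significant at the 1% level".

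If hysteresis is found, the section first says that an effect-compartment model will be explored. The model paragraph goes further: the concentration covariate is the observed value without hysteresis and the effect-compartment prediction with it. The negative-QT criterion (upper 90% bound for ddQTcF below 10 msec at the largest geometric mean Cmax) is then read from that model.

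Two other places matter. Section 2.4.2 forms ddQTcF by subtracting the mean change "of all placebo subjects at each postdose time point". Section 8.1 extracts ECGs at "0.5, 1, 2, 3, 4, 5, 6, 8, 12, 24, 36, 48, 60, and 72 hours after dosing", with "A window of ± 5 minutes around each time point".

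The SAP does not say whether the test is run by dose or on all doses pooled.

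**The concern.** The Wilcoxon test holds its level when the two times are fixed in advance and each subject's difference is an independent draw, symmetric about zero under the null. Neither requirement is met.

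- **Selection.** Umax is found by searching the same profile that is then tested. On a mean curve the mean difference, Umax minus Tmax, cannot be negative. Taken per subject, every non-zero difference is positive.
- **Shared placebo error.** The same estimated placebo mean is subtracted from every active subject at a given time. Its error shifts all the differences together, and a one-sample test treats it as known.

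The 30-minute condition adds little protection on a grid whose closest times are 30 minutes apart, so the 5 msec condition is the main guard. A true direct QT effect opens that guard, and this is when the 10 msec decision is close. What is at stake is whether the primary model changes its concentration covariate although there is no delay.

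**Working it through.** **Inputs from the SAP.** 14 post-dose times; 10 subjects per group, so 50 active and 10 placebo; level 1%, one-sided; thresholds of 5 msec and 30 minutes.

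**Assumptions, not in the SAP.** Normal QTcF errors, independent over time unless stated, with SD 5 or 8 msec; a PK profile whose mean peaks at 3-4 h; an effect proportional to concentration with no delay.

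**1. The 30-minute condition.** Gaps between scheduled times are 0.5, 1, 1, 1, 1, 1, 2, 4, 12, 12, 12, 12 and 12 h. The smallest is exactly 30 minutes, so on nominal times the condition excludes only Umax = Tmax. On actual times it can bind: samples at 35 and 55 minutes are within the ±5-minute windows and only 20 minutes apart. It can also bind if Tmax is averaged over subjects and falls off the grid. In one set of runs, mean Tmax was within 30 minutes of Umax without equalling it in 14-26% of trials.

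**2. The plan's 1%, reproduced.** For a fixed pair of times and a known placebo mean, the exact signed-rank test at n = 10 rejects when the positive rank sum is at least 50 of 55, with probability 10/1024 = 0.98%. At n = 50 the cut-off is 878 of 1,275, also 0.98%. Simulation gave 0.89% and 1.02%.

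**3. Selection alone.** With a flat response and the placebo mean still known, choosing Umax as the maximum of the group mean raises rejection to 6.4% (n = 10) and 7.6% (n = 50). A per-subject maximum gives 99.6% and 100%.

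**4. Placebo error alone.** For error SD σ, the mean active difference has standard error σ√(2/n), and the placebo difference adds σ√(2/10) = 0.447σ.

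- n = 50: the true SD is σ√(0.04 + 0.20) = 0.490σ, against 0.200σ assumed, a ratio of 2.45. Then 2.326/2.45 = 0.95, giving a normal tail of about 17%.
- n = 10: the ratio is √2. On a t scale with 9 df, 2.821/1.414 = 1.99, giving about 4%.

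Simulated fixed pairs with zero or constant effect rejected in 15-17% and 3-4%.

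**5. Both together.** With a zero or constant effect and Umax from the group mean, the Wilcoxon step rejects in 17-21% (n = 10) and about 57-59% (n = 50).

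**6. The full rule with a direct effect and no delay**, 1,500 trials per row. The effect was scaled to a concentration of 0.62 per mg, while the mean profile peaks at 0.746. Effect settings of 6, 8 and 10 msec therefore mean mean-curve peaks at 36 mg of 6 × 0.746/0.62 = 7.2, 9.6 and 12.0 msec.

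| Peak (msec) | SD | Top dose, mean curve: Wilcoxon / full rule | Pooled, mean curve: Wilcoxon / full rule | Per subject, full rule: top / pooled |
|---|---|---|---|---|
| 7.2 | 5 | 9.5% / 8.0% | 36.9% / 10.9% | 67.3% / 25.8% |
| 7.2 | 8 | 11.0% / 9.3% | 43.5% / 20.3% | 70.9% / 43.0% |
| 9.6 | 5 | 7.4% / 7.1% | 34.9% / 16.5% | 70.9% / 39.6% |
| 9.6 | 8 | 9.3% / 8.3% | 39.8% / 23.5% | 74.3% / 52.5% |
| 12.0 | 5 | 4.9% / 4.8% | 32.3% / 22.4% | 64.5% / 54.7% |
| 12.0 | 8 | 8.5% / 8.2% | 36.9% / 25.5% | 77.7% / 60.4% |

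The Monte Carlo error at 8% is √(0.08 × 0.92/1,500) = 0.7 percentage points.

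Pooling makes the 5 msec guard stricter. The mean active dose is (4 + 8 + 16 + 24 + 36)/5 = 17.6 mg, so under a dose-proportional effect it needs 5 × 36/17.6 = 10.2 msec at 36 mg.

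**7. Sensitivity.** Other runs at 8-12 msec with SD 5-6 msec and other assumed PK profiles gave 5-11% (top dose) and 15-29% (pooled) on mean curves, and 38-89% per subject. Serial correlation of 0.8-0.95 per hour lowered the mean-curve rates to 3-6% and 9-19%. With zero effect, the mean-curve full rule fired in 2.5-5.9% (top dose) and 2.1-10% (pooled).

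**8. Consequence of a false declaration.** In no-delay trials where the rule fired, an effect-compartment model was fitted and compared with the direct model. Predicted ddQTcF at the 36-mg Cmax moved by about 0.1-0.4 msec on average. The 95th percentile was about 0.5 msec in one set of runs and 0.7-2.3 msec in another. In the first set, the median fitted rate constant lay at the fastest value allowed, which is nearly the direct model. That set used simple least squares with known PK profiles and point estimates only.

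**The case against.** The strongest reply is that a false declaration does little harm. An effect-compartment model contains the direct model as its fast-equilibration limit, so without a delay it should fall back towards observed concentrations, and step 8 agrees. The secondary analysis in section 8.3 also models ddQTcF on measured concentrations regardless of the hysteresis finding, with 90% intervals at each dose's mean Cmax. And missing real hysteresis may be the worse error in a QT assessment. All this stands, and it limits the severity. It does not make the 1% true. Nor does the secondary model replace the primary dQTcF model, on which the 10 msec criterion is set.

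Three stronger readings are tempting, and the SAP does not support them.

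- A reader might take the per-subject rates (26-78% in the table) as the rule's error rate. The opening reference to an average or median favours mean or median curves, so the lower figures are the fair headline. Pooling over doses is left open rather than stated.
- A reader might infer that the 30-minute limit can never bind. That holds only for nominal times.
- A reader might infer that the QT conclusion would be overturned. No calculation shows that.

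The sentence about exploring an effect-compartment model is softer than a switch, but the model paragraph makes the covariate conditional on the finding.

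**Conclusion.** The stated 1% is not the error rate of the Wilcoxon step, because the test ignores both the selection of Umax and the error in the shared 10-subject placebo mean. With a direct effect of about 8-12 msec at 36 mg and no delay, the full rule fires in roughly 3-11% of trials on the top-dose mean curve and 9-29% if doses are pooled. These rates depend on the assumed SD, PK profile and error correlation, none of which the SAP gives. The excess over 1% appeared under every set of assumptions tried.

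A false declaration changes the covariate in the primary model, with a usually small shift at Cmax. Its effect on the width of the bootstrapped interval was not studied. This is a minor-to-moderate point: worth correcting before unblinding, not a threat to the design.

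**What to change.** In SAP section 8.3:

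- State that Tmax and Umax are read from the mean (or median) profile of each dose group, and that the test is run by dose group.
- Obtain the p-value by simulating active and placebo subjects from the fitted direct-effect model, recomputing the placebo mean and reselecting Umax in each replicate. Otherwise remove the 1% claim and call the rule a descriptive screen. A Bonferroni correction over 13 alternative times is no substitute: 0.01/13 = 0.077% is below the smallest attainable p at n = 10, which is 1/1,024 = 0.098%.
- Whenever an effect-compartment model is used, report the primary dQTcF model with observed concentrations, and its 10 msec criterion, beside it.

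A minimum lag counted in sampling intervals is not advised. The intervals run from 0.5 to 12 h, so it could hide a real delay.

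The cost is SAP wording and a modest simulation, with no new data. The downside is slightly lower sensitivity to a true short delay.
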